7.5 Follow-Up Visits

7.5.1 Follow-Up Visits for Responders (These visits may be completed depending on the date of enrollment relative to the end of study.)

7.5.1.1 Month 1 Follow-Up Visit (+/- 2 weeks)

- Update Medical History
- Update Psychiatric Medication Log
- Update Somatic Therapies Log
- Vitals (BP, heart rate, weight)
- Evaluation for Adverse Events or Serious Adverse Events
- Psychiatric Evaluation
- Patient Rated Behavioral Scales
 - QIDS-SR-16 (to be completed first)
 - o GSE-MY
 - o SMCQ
 - o PGI-S & PGI-I
 - o QOLS
 - o PRISE
 - o CPFQ
- Clinician Rated Behavioral Scales
 - MADRS
 - o CSSRS
 - o YMRS
 - o BPRS
 - o CGI-S & CGI-I
 - CADSS
- Cognitive Assessments

- o MoCA
- o COWAT
- o HVLT-R
- o Stroop

7.5.1.2 Month 3 Follow-Up Visit (+/- 2 weeks)

- Update Medical History
- Update Psychiatric Medication Log
- Update Somatic Therapies Log
- Vitals (BP, heart rate, weight)
- Evaluation for Adverse Events or Serious Adverse Events
- Psychiatric Evaluation
- Patient Rated Behavioral Scales
 - QIDS-SR-16 (to be completed first)
 - GSE-MY
 - o SMCQ
 - o PGI-S & PGI-I
 - o QOLS
 - o PRISE
 - o CPFQ
- Clinician Rated Behavioral Scales
 - MADRS
 - o CSSRS
 - o YMRS
 - o BPRS
 - o CGI-S & CGI-I
 - o CADSS
- Cognitive Assessments
 - o MoCA
 - o COWAT
 - o HVLT-R
 - Stroop

7.5.1.3 Month 6 Follow-Up Visit (+/- 2 weeks)

- Update Medical History
- Update Psychiatric Medication Log
- Update Somatic Therapies Log
- Vitals (BP, heart rate, weight)
- Evaluation for Adverse Events or Serious Adverse Events
- Psychiatric Evaluation

- Patient Rated Behavioral Scales
 - QIDS-SR-16 (to be completed first)
 - o GSE-My
 - o SMCQ
 - o PGI-S& PGI-I
 - o QOLS
 - o PRISE
 - o CPFQ
- Clinician Rated Behavioral Scales
 - MADRS
 - o CSSRS
 - YMRS
 - o BPRS
 - o CGI-S & CGI-I
 - CADSS
- Cognitive Assessments
 - o MoCA
 - o COWAT
 - o HVLT-R
 - Stroop

7.5.2 Follow-Up Phone Call for Non-Responders

7.5.2.1 Month 1 Follow-Up Phone Call (+/- 2 weeks)

- Evaluation for Adverse Events or Serious Adverse Events
- Evaluation for additional ECT, ketamine, psychotropic treatment(s) performed
 - o Update Somatic Therapies Log
 - Update Psychiatric Medications Log
- Patient Rated Behavioral Scale
- PGI-S & PGI-I
- Completion of QIDS
- Completion of MADRS

7.5.3 End of Study participation for the subject

A subject will be considered as achieving End of Study when:

- Subject completes all treatment visits and follow-up visits, according to Responder/Non-Responder classification
- Subject withdraws full consent
- Subject is Lost to Follow Up
- Subject Expires
- Clinician discretion

An End of Study eCRF will be completed for each subject randomized to treatment.

7.6 Non-Compliance

A patient can be withdrawn from the study for non-compliance, per investigator discretion, if they miss two or more consecutive treatments during the acute treatment phase of the study.

7.7 Subject Withdrawal

Subjects may withdraw from study participation or from the study treatment at any time at their own request, or they may be withdrawn at any time at the discretion of the investigator for safety or behavioral reasons, or the inability of the subject to comply with the protocol required schedule of study visits or procedures at a given study site. If the subject elects to discontinue participation in the study or to discontinue study treatment, the investigator should:

- Inquire about the reason for withdrawal
- Request the subject to return for an EOT Visit to assess AEs/SAEs, safety endpoints, outcome events, vital status
- Follow-up with the subject regarding any unresolved adverse events.

If the subject withdraws from the trial and also withdraws consent for disclosure of future information, no further evaluations should be performed and no additional data should be collected. Adequate documentation of this request should be obtained and retained in the subject's source file. True withdrawal of consent should be subject initiated and in writing. The sponsor may retain and continue to use any data collected before withdrawal of consent.

7.8 Lost to Follow-Up

Contact information from the patient, including an emergency contact will be obtained at the time of screening. This information will be reviewed and verified at each clinic visit and telephone contact.

Patients will be considered lost to follow-up (LTFU) after the End of Treatment phase, when one of the following is met:

- For Non-Responders in the one month Follow-Up Phase patients will be considered LTFU after 3 attempts to contact the patient.
- For Responders in the Follow-Up Phase patients will be considered LTFU only after the Month 6 Visit, or at the end of study, whichever comes first.

For each missed visit, study staff should make three attempts to contact the patient as soon as possible at various intervals. The site should access medical records, other health care professionals, institutional databases and any other means to contact the patient as allowed by their IRB. All attempts to contact the patient should be documented in the research chart and medical records.

7.9 Study Termination

This study may be terminated or suspended at any time. If the study is terminated or suspended, the sponsor will promptly inform the investigators / institutions and PCORI.

Confidential Page **27** of **40** Protocol V7.0 16Feb2022

The IRB should be promptly informed and provided the reasons(s) for the termination or suspension by the sponsor and by the investigator / institution, as specified by the applicable regulatory requirement(s).

8. Safety Monitoring and Reporting

Patients will be closely monitored for adverse events (AEs) or serious adverse events (SAEs), including worsening of depression symptoms. Study investigators will be able to modify treatment or remove patients from the trial based on their clinical discretion and specific patient outcomes.

An adverse event is the development of an undesirable medical condition or the deterioration of a pre-existing medical condition following or during exposure to a pharmaceutical product, whether or not considered causally related to the product. An undesirable medical condition can be symptoms (e.g., nausea, headache, fatigue, blurry vision) or signs (e.g., rapid or irregular heart rate, hypertension). In clinical studies, an AE can include an undesirable medical condition occurring at any time after the informed consent is signed even if no study treatment has been administered.

Assessment of adverse events, including grading of severity and attribution to research will start at the time of consent. AEs will be evaluated at each visit.

For adverse events (AEs), the following guidelines will be used to describe severity.

- **Mild** Events or symptoms that are easily tolerated and do not interfere with the participant's daily activities.
- Moderate Events or symptoms that result in a low to moderate level of inconvenience or concern with normal daily activities. Moderate events may cause some interference with functioning.
- **Severe** Events or symptoms that interrupt a participant's usual daily activity and may require drug therapy or other treatment. Severe events are usually potentially life-threatening or incapacitating. Of note, the term "severe" does not necessarily equate to "serious"

Note: As of 1/1/2018, AEs that are classified as mild, do not need to be reported in the patients chart or the eCRF, per Investigator discretion. AEs classified as moderate or severe, as assessed by an Investigator, need to be reported in the patients chart and the eCRF.

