All patients will complete self-reported cognitive assessments, depression questionnaires, and quality of life scales at the Baseline Visit/Visit 1 and throughout the acute treatment phase of the study (see Schedule of Events). Diagnostic interviews and clinician rated scales will also be performed at regular intervals throughout the acute treatment phase.

After the acute treatment phase, all patients will complete an EOT visit within 3 days of their last study treatment and will be classified as either a responder or a nonresponder. Patients may continue to receive ECT or ketamine clinically after the EOT visit, but this will mark the end of the acute treatment phase of the study. If the patient is a responder, any ECT or ketamine treatments administered after the EOT visit will be recorded in the follow-up phase. If the patient is not a responder they will receive a phone call one month after the End of Treatment Visit for completion of PGI-I, PGI-S, QIDS and MADRS, and record any ECT or ketamine treatments administered after the EOT visit. This will conclude their participation in the study and they will be

Confidential Page **13** of **40** Protocol V7.0 16Feb2022 treated clinically.

Responder: a patient who achieves a \geq 50% decrease in their QIDS-SR-16 score from Baseline/Visit 1 to the End of Treatment visits. Responders may continue in the study for three follow-up visits at one month, three months, and six months after the EOT Visit, depending on the date of enrollment relative to the end of study. They will continue naturalistic treatment with a clinician of their choice.

Non-Responder: a patient who achieves <50% decrease in their QIDS-SR-16 score from Baseline/Visit 1 to the End of Treatment Visit. Non-responders will receive a phone call at one month after the EOT Visit. They will be exited from the study after the one month phone follow-up visit and will not be contacted or seen for the three and six month follow-up visits. They will continue treatment with the clinician of their choice.

Early Completion of Acute Treatment Phase

The investigator or patient can choose to stop treatment at any time. Investigators will monitor patients closely for signs of improvement, remission, or decline. The investigator will use his or her discretion and clinical judgment to determine if a patient should stop treatment and be scheduled for an End of Treatment Visit.

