Investigators may decide to stop treatment for patients who show improvement after less than nine ECT treatments or six ketamine treatments. These patients should be scheduled for an End of Treatment Visit and if they are found to be responders will participate in the follow-up visits.

Investigators may also decide to stop treatment for patients who decline or have worsening depression or suicidality during the acute treatment phase. These patients should be scheduled for an End of Treatment Visit and be evaluated for response. (These patients are unlikely to be classified as responders.

If an outpatient has worsening depression that requires psychiatric hospitalization, the patient may continue in the study at investigator discretion. These patients can receive study ECT or ketamine treatments as an inpatient.

4. Outcome Measures

To avoid potential bias, the patient assessments and the clinician assessments should be completed independently and without reference to one another. The research coordinator or clinician administering the questionnaires should not view the patient's responses on patient rated scales. (They should, however, remind the patient to answer all questions and not leave any questions blank.)

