6.3.2 Prohibited Medications

Patients should not be enrolled in the study if they are taking any medication that is contraindicated for ECT or ketamine treatment.

Changes in medical history and concomitant medications will be assessed at each visit and patients may be withdrawn from the study at any point if they are taking prohibited medication.

7. Study Procedures

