7.3.3 Completion and/or Early Termination of Treatment Phase

Investigators can end the treatment phase early, before the maximum number of treatments are completed, if:

- The clinician feels the patient has achieved a sustained remission (QIDS-SR-16 score <5 on two consecutive assessments) or the clinician determines additional treatments are not clinically warranted
- The patient has worsening depression, severe psychotic symptoms, or becomes suicidal

If these situations occur the patient should be scheduled for an End of Treatment Visit. The patient can decide not to continue treatment for any reason. They should be encouraged to complete an End of Treatment Visit.

Confidential Page **22** of **40** Protocol V7.0 16Feb2022

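### Section 8 permits, without requiring, removal of a worsening patient before the EOT score is taken, and the SAP's imputation as listed may not correct the loss

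*Protocol*

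**What the plan says.** Protocol Section 8, just after naming worsening depression as something to monitor, says: "Study investigators will be able to modify treatment or remove patients from the trial based on their clinical discretion and specific patient outcomes". Section 7.5.3 opens its list with "A subject will be considered as achieving End of Study when". One entry is simply "Clinician discretion", separate from completion, withdrawn consent, loss to follow-up and death, and with no EOT condition attached.

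Other sections direct an EOT visit for the same patient. Section 3 says that "all patients will complete an EOT visit within 3 days of their last study treatment", and that the number of treatments received makes no difference. It adds: "Investigators may also decide to stop treatment for patients who decline or have worsening depression or suicidality during the acute treatment phase", and then asks that these patients have an EOT visit and be assessed for response. Section 7.3.3 repeats it for early stopping: "If these situations occur the patient should be scheduled for an End of Treatment Visit". Section 7.4 sets the same three-day window for patients who stop early.

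Section 7.7 allows withdrawal by the subject or by the investigator, but words its EOT request for a subject who chooses to stop.

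In the SAP (Analysis of primary endpoint), one treatment and one acute-phase QIDS-SR-16 score are enough to enter the mITT set. How a patient in that set without an EOT score is handled in the principal analysis is not stated. Multiple imputation is a sensitivity analysis. It names baseline characteristics, baseline QIDS-SR-16 and MADRS, and their percent changes at EOT. It names neither arm nor the on-treatment scores, which Protocol Sections 4.1, 7.3.1 and 7.3.2 show are collected.

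**The concern.** The primary outcome exists only if the EOT QIDS-SR-16 is taken. Treatment is open label, and Sections 6.1.1 and 6.1.2 have clinicians judge response before each treatment, so the person deciding on removal knows both the arm and the patient's course. If a worsening patient leaves without an EOT score, missingness depends on both.

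Removing poor responders mainly from ketamine would raise the chance of a false claim of non-inferiority. Removing them mainly from ECT would hide true non-inferiority. The documents do not show which is more likely.

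A patient removed before EOT has no EOT percent change. The imputation as listed would then rest on baseline data alone for that patient and would not see the decline that led to removal.

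**Working it through.** **Plan's own figures.** Inputs from the SAP sample-size section: ECT 50%, margin 10 points, one-sided alpha 0.025, 346 evaluable (173 per arm) of 400 randomised. Farrington-Manning power is Φ[(Δ + 0.10 − 1.96·s0)/s1]. Here Δ is ketamine minus ECT, s0 uses the restricted estimates at −0.10, and s1 the unrestricted rates. At 173 per arm this gives 80.1% for 55% v 50% (SAP 80%), 96.4% for 60% v 50% (SAP 96.4%), and 80.2% for 60% v 50% with a 5-point margin (SAP 80.3%). At 40% v 50% the false non-inferiority rate is 2.5%.

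**Effect of removal on outcome.** Assumptions, not in the documents: 200 − 173 = 27 patients are lost per arm; r of them are removed on outcome and the rest are lost at random; a share u of the removed would have responded; patients without an EOT score are left out of the test. The analysed rate is then (p − u·r/200)/(1 − r/200), with n = 173.

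Example, ketamine r = 10, u = 0: 0.40/0.95 = 0.421, so Δ = −0.079. With s0 and s1 both about 0.053, the rate of declaring non-inferiority is 5.9%.

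| Removed on outcome | False non-inferiority at 40% v 50%, u = 0 | u = 0.2 |
|---|---|---|
| none | 2.5% | 2.5% |
| ketamine only, 2 | 3.0% | 2.7% |
| ketamine only, 4 | 3.5% | 3.0% |
| ketamine only, 10 | 5.9% | 3.9% |
| ketamine 10, ECT 5 | 3.6% | 2.8% |
| ketamine 10, ECT 8 | 2.5% | 2.3% |
| 10 in each arm | 2.0% | 2.0% |

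ECT-only removal lowers false non-inferiority and costs power. At 55% v 50%, power falls from 80% to 77%, 74% and 64% for r = 2, 4 and 10 with u = 0, and to 78%, 77% and 71% with u = 0.2.

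The range for u is plausible. With on-treatment and EOT change taken as bivariate normal, response among the worst 5% of on-treatment scores at p = 0.40 is 18%, 12% and 3.5% for correlations 0.3, 0.4 and 0.6.

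**Imputation.** Simulation: 200 per arm, true difference −10 points, 27 lost per arm, of whom the 10 ketamine patients with the worst on-treatment scores are removed and all others are lost at random. Correlation of on-treatment with EOT change is 0.4 or 0.6, baseline is uninformative, and there are five imputations. Mean estimated differences:

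- Removed patients left out: −8.6 or −8.1.
- Imputation with arm, without on-treatment scores: about −8.7 to −8.0, the same bias as leaving them out.
- Imputation without arm or on-treatment scores: about −7.4 to −7.1.
- Imputation with arm and on-treatment scores: about −10.

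The extra shift without arm is mostly dilution. With 27/200 = 13.5% of each arm filled in from a pooled distribution, the difference shrinks by a factor 0.865 (−8.6 × 0.865 = −7.4). Purely random loss would shrink it too (−10 × 0.865 = −8.65), so omitting arm is a separate weakness of the model as listed.

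**The case against.** The strongest reply is that no real conflict exists. The specific rules in Sections 3, 7.3.3 and 7.4 cover exactly this patient, while Section 8 is a general safety sentence that never waives the EOT visit. The clinician-discretion entry in 7.5.3 also serves the follow-up phase, and 7.7 mentions investigator withdrawal just before its EOT request. This stands in part: a site can remove a patient and still hold the visit. But Section 8 sets removal from the trial beside changing treatment as a separate option, and neither 7.5.3 nor the wording of 7.7 secures the EOT score when the investigator decides.

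Sections 6.3.2 ("patients may be withdrawn from the study at any point if they are taking prohibited medication") and 7.6 ("A patient can be withdrawn from the study for non-compliance, per investigator discretion, if they miss two or more consecutive treatments") might be read as further routes to removal on outcome. They are not: one concerns prohibited medication, the other missed treatments.

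On the SAP, the list of imputation variables need not be exhaustive. Protocol Section 9 provides pattern-mixture modelling for non-ignorable missing data, although the SAP places it only in its text on secondary endpoints. The mixed model for QIDS-SR-16 does use on-treatment scores, but as a secondary analysis. So it would be too strong to say that the plan cannot correct the loss.

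On size, the removal counts are assumed. An exact calculation puts the base error at 2.7%, so the smallest ketamine-only case is no larger than the test's ordinary size error. The 5.9% needs ten removals in ketamine, none in ECT, and no would-be responder among them.

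**Conclusion.** The point holds as a permitted, not a required, loss of the primary outcome, with an imputation that as listed may not correct it. The effect is small for 2 to 4 removals in one arm, material for about ten in one arm only, and almost nil when removal is near equal. These sizes rest on assumed counts, on 27 losses per arm, on u between 0 and 0.2, and on leaving out patients without an EOT score, which the SAP does not specify. Direction is unknown.

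Two stronger inferences are not supported. The documents do not say that worsening patients leave without an EOT visit; several sections direct the opposite. Nor does the width of the worst-best to best-worst range count against Section 8. At 15% missing per arm it is 15 + 15 = 30 points, but that reflects total attrition; ten removals in one arm contribute 10/200 = 5 points.

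This is a cheap improvement of modest severity.

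**What to change.** 1. Protocol. In Section 8, say that study treatment may be stopped but the patient stays in the study and completes the EOT visit with QIDS-SR-16. In 7.7, apply the EOT request to investigator-initiated withdrawal too. In 7.5.3, say that clinician discretion does not end participation before the EOT visit. Use the same wording in 6.3.2 and 7.6 for consistency.
2. SAP. Add arm and the on-treatment QIDS-SR-16 and MADRS scores to the imputation model. Tabulate missing EOT outcomes by arm and by who made the decision.

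Cost: wording in five protocol sections, one EOT visit per stopped patient, and data already collected. Investigators can still stop treatment at any time for safety. Test, margin, alpha and sample size do not change. Some stopped patients will still decline the visit, so the imputation change is needed as well.

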Ketamine shows promise as a treatment for TRD, but there is an evidence gap in its use as an alternative to ECT. Ketamine is a sedative/analgesic and general anesthetic approved by the FDA for human and veterinary use. It is an antagonist of the N-methyl-d-aspartate (NMDA) receptors in the brain and decreases the neurotransmission of glutamate (the main excitatory neurotransmitter) via the NMDA

Confidential Page **12** of **40** Protocol V7.0 16Feb2022

receptor.

Single infusion of a sub-anesthetic dose of ketamine has shown rapid but transient reversal of TRD symptoms. A number of open label studies done so far indicate that repeated ketamine infusion treatment results in responses similar to that of ECT (40). Ketamine can lead to symptoms of dissociation, perceptual disturbances, or even psychotic like symptoms (33) although these are seen infrequently at sub-anesthetic doses used in the treatment of TRD and are rapidly reversed after stopping the infusion.

Currently, there are no formal randomized trials with detailed clinical and demographic data to provide direct comparative efficacy evidence between ECT and ketamine treatment. This study will provide such data and help to fill the evidence gap for efficacy of ECT and ketamine treatment for TRD.

3. Study Design

This is a prospective randomized open-label 2-arm (1:1) clinical trial of TRD with either ECT or ketamine treatment. Given the nature of ketamine and ECT treatments randomization and treatment arms cannot be blinded at the clinician or patient level.

After screening and evaluation of inclusion/exclusion criteria, patients will be randomized to either ECT three times per week or ketamine two times per week. This acute treatment phase will last between three to five weeks. This timeframe allows for changes in the treatment schedule due to clinician discretion or the patient's schedule. Patients may respond or remit to ECT or ketamine before they have completed all treatment visits and therefore may not undergo the full nine visits (for ECT) or six visits (for ketamine). Investigators will closely monitor patients and may adjust treatments during the acute treatment phase at any time. All patients, regardless of how many treatment visits have been completed, should complete an End of Treatment Visit (EOT).

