8.1 Unexpected Adverse Events

The following adverse events will be collected from the time of randomization for the study:

Adverse events that are not listed in the current labeling for ketamine (Ketalar Product Information) or ECT. This includes events that are similar to those on the labeling but differ from the event because of greater severity or specificity.

The following AEs should be captured and recorded on the AE form:

- Prolonged seizure
- Tardive seizure (late occurring)
- Delirium (prolonged)
- Psychosis (prolonged)
- Suicide Attempt
- Severe hypertension (prolonged)
- Dissociation (prolonged)
- Substance abuse (new onset/reoccurrence)
- Clinically significant arrhythmia
- Pregnancy
- Other AEs per Investigator discretion

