Since the QIDS-SR16 score itself is repeatedly measured over time, a linear mixed-effects model will be applied to estimate its trajectories of the two groups during the acute treatment phase. The model will include measurement time, treatment group, their interaction, and site as fixed effects, and a Gaussian random intercept at the patient level. Baseline patient characteristics with statistically significant differences between the two groups may be also included as fixed effects if deemed necessary. The covariance matrix of the repeated measurements within each patient will be selected from the candidates of compound symmetric, first-order autoregressive (AR1), Toeplitz, and unstructured structures using the information criterion. Least-square estimates will be derived to estimate the QIDS-SR16 mean at each visit by group, and corresponding linear contrasts can be used for group comparison at each visit. Since the responders will be further followed at months 1, 3 and 6 after the acute phase, another linear

mixed-effects model with the same formation will be applied to the subgroup of responders for their longitudinal QIDS-SR-16 data until the end of the follow up phase. The model for the change of QIDS-SR-16 score will include the score changes as the dependent variable and further include the baseline QIDS-SR-16 score as a covariate. For the other continuous secondary endpoints measured longitudinally, their analyses will follow the analysis of the QIDS-SR-16 score. These endpoints include various patient and clinician rated scales for depression, suicidality, and cognitive function (e.g., MADRS and YMRS).

For the cross-sectional endpoints such as the MoCA rating assessed at the end of treatment visit, linear regression will be used to analyze and compare the data between the two groups. Generalized linear regression (e.g., logistic regression or ordinal logistic regression) will be applied to binary or multi-categorical outcomes, depending on the variable type of the outcome.

Analysis of safety endpoints. Mortality will be summarized as percentage by group, and the chi-squared test will be used to compare the mortality rates between the two groups. If the expected number of deaths is small, the Fisher's exact test will be used instead. The other dichotomous safety outcomes such as the unexpected adverse events, adverse events causing treatment discontinuation and serious adverse events will be analyzed in the same manner.

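### The SAP tests unexpected adverse events between unblinded arms with no severity limit, while the Protocol contradicts itself on whether mild ones must be recorded

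*Protocol*

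**What the plan says.** **Recording by grade.** The note at the end of the opening text of Protocol section 8, dated from 1/1/2018, says that "AEs that are classified as mild, do not need to be reported in the patients chart or the eCRF, per Investigator discretion". It continues: "AEs classified as moderate or severe, as assessed by an Investigator, need to be reported in the patients chart and the eCRF".

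**Recording of unexpected events.** Section 8.1 opens with "The following adverse events will be collected from the time of randomization for the study". It defines them as "Adverse events that are not listed in the current labeling for ketamine (Ketalar Product Information) or ECT", and includes events like the labelled ones but more severe or more specific. The definition has no lower limit on severity. The section then names events to be captured on the AE form, such as prolonged seizure, suicide attempt and clinically significant arrhythmia, and closes the list with "Other AEs per Investigator discretion".

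**Other safety data.** Section 8.2 requires collection of events that lead to discontinuation, and section 8.3 requires collection of all serious AEs from consent. Each has its own rule.

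**Analysis.** The SAP (Analysis of safety endpoints) compares mortality by chi-squared or Fisher's exact test and says that the other dichotomous outcomes, "such as the unexpected adverse events, adverse events causing treatment discontinuation and serious adverse events will be analyzed in the same manner". SAP Table 1 lists unexpected adverse event as a safety endpoint, again with no grade attached.

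**Blinding.** Protocol section 3 states that "randomization and treatment arms cannot be blinded at the clinician or patient level".

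**The concern.** A between-arm test of event proportions is interpretable when an event has the same chance of reaching the database in both arms. For a mild unexpected event, that chance may rest on the choice of an investigator who knows the treatment. If the choice differs by arm, the test compares recording as well as harm. It can show a difference that does not exist or hide one that does.

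There is also a gap on the other side. Moderate and severe AEs must be recorded, but the AE categories named in the SAP are unexpected, discontinuation and serious events. A moderate or severe labelled event that is not serious and does not stop treatment has no named AE comparison. Both treatments have known side effects, which Protocol section 2 describes, so these events matter to patients and clinicians choosing between them.

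**Working it through.** **Step 1: which rule covers which event?**

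| Event | Section 8 note | Section 8.1 | Named AE test in the SAP |
|---|---|---|---|
| Mild, unexpected | discretionary | collected | yes |
| Mild, labelled, not more severe or specific than labelled | discretionary | not covered unless named or added at discretion | no, unless it stops treatment or is serious |
| Moderate or severe, unexpected | mandatory | collected | yes |
| Moderate or severe, labelled, non-serious, treatment continues | mandatory | not covered unless named or added at discretion | no |

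The first row is the contradiction. Neither section says which prevails, and the SAP tests the result either way. The last row is the gap.

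**Step 2: what could the first row do to the test?** The documents give no AE rate, no recording rate and no alpha for safety tests, so there is no stated figure to reproduce. What follows is an illustration. Only the 200 patients per arm comes from the documents (Protocol synopsis).

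Assumptions:
- s = 5% of each arm has a moderate or severe unexpected AE, always recorded.
- m = 10%, 20% or 40% of each arm has only a mild unexpected AE.
- r is the share of mild events recorded, which may differ by arm.
- The test is the uncorrected chi-squared test, two-sided 0.05, with rejection probability by exact binomial enumeration.

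Recorded proportion in an arm = s + m × r. For m = 20% and r = 40% versus 60%, this is 0.05 + 0.20 × 0.40 = 13% and 0.05 + 0.20 × 0.60 = 17%.

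Chance of a significant result when true rates are equal (recorded proportions in brackets):

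| m | r 50% vs 50% | r 40% vs 60% | r 30% vs 70% |
|---|---|---|---|
| 10% | 4.8% (10 vs 10) | 9.9% (9 vs 11) | 26.1% (8 vs 12) |
| 20% | 5.1% (15 vs 15) | 20.4% (13 vs 17) | 61.9% (11 vs 19) |
| 40% | 5.0% (25 vs 25) | 45.6% (21 vs 29) | 96.3% (17 vs 33) |

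With only moderate or severe events counted (5% in each arm), the chance is 4.8%.

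The artificial gap is m × (difference in r), so it shrinks with m. At m = 2% and r = 30% versus 70%, it is 0.02 × 0.40 = 0.8 percentage points.

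**Step 3: can real harm be hidden?** Take true mild rates of 20% versus 40%, with s = 5%. Fully recorded, the arms show 25% versus 45%, and the test detects the difference with probability 98.9%. If 70% of mild events are recorded in the first arm and 35% in the second, the arms show 0.05 + 0.20 × 0.70 = 19% and 0.05 + 0.40 × 0.35 = 19%. The probability of detection falls to 5.1%.

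**The case against.** The strongest reply is that section 8.1 bears the name of the SAP endpoint and says that these events are collected. On the usual reading that the specific rule beats the general one, mild unexpected events were always to be recorded and the note never touched them. That reading is reasonable, but the Protocol does not state it. The note contains no exception for section 8.1, and a site could follow either.

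Second, few events are likely to be both mild and unexpected. Labelled complaints are outside the endpoint unless they exceed the label, and most named events carry a qualifier such as prolonged or severe. This stands, and it means that the larger values of m above may be too high.

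Third, the note applies to both arms alike. This also stands: recording that depends on the arm is plausible in an open-label trial, but nothing in the documents shows it.

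Fourth, PRISE, a self-report of side effects, is scheduled seven times in each arm from baseline through the end-of-treatment visit and is a secondary endpoint in SAP Table 1. It does not depend on investigator recording, so tolerability has a second source. It is still unblinded self-report, and it does not repair the unexpected-AE test.

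Fifth, restricting the test to moderate and severe events moves the discretion from recording to grading, because the same investigators assign the grade. That limits what the fix can achieve.

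**Conclusion.** The point holds for one endpoint. For mild unexpected events, the section 8 note and section 8.1 conflict. The SAP's test of unexpected AEs takes whatever was recorded, in an unblinded trial, and so is open to distortion if recording differs by arm. Separately, non-serious moderate or severe labelled events that do not stop treatment must be recorded but have no named AE comparison.

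The size cannot be derived from the documents. The percentages above rest wholly on assumed event and recording rates. They show only that the effect is nil with equal recording and can be large otherwise.

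Four stronger conclusions might be inferred, and the documents do not support them:
- **The whole safety comparison is compromised.** Mortality and vital signs do not depend on the note, and discontinuation and serious AEs have their own collection rules.
- **Bias is present.** That needs recording that depends on the arm. Habits that differ only between sites are not enough, since a site's habit applies to whichever arm a patient is randomised to.
- **Moderate and severe events were mandatory from the first patient.** The rule is dated from 1/1/2018. The current text gives neither the earlier rule nor an enrolment start date.
- **The mandatory data go unused.** Moderate and severe events that are unexpected, serious or lead to discontinuation are compared, and the SAP's list is worded as examples.

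**What to change.** 1. In the Protocol, reconcile the section 8 note with section 8.1, stating which rule governs a mild unexpected event. State also which rule sites followed before 1/1/2018, if any patients were enrolled by then.
2. In the SAP, base the between-arm AE comparison on moderate or severe events, expected or unexpected, plus the events named in section 8.1 whatever their grade. Leave the open-ended last item of that list out of the named set, because it is discretionary. Keep the discontinuation, serious AE and mortality comparisons as they are.
3. Report other mild events by arm without a test, and name PRISE as the scheduled tolerability comparison.

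The cost should be wording only, since the Protocol already calls for severity grading. There are three drawbacks. Mild events outside the named list leave the formal test. Adding labelled events makes this a different endpoint from unexpected AEs, so the SAP should say so and still tabulate unexpected AEs descriptively. And because unblinded investigators assign the grade, the bias is reduced rather than eliminated. No change of wording can recover mild events that were never recorded.
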